#### **4.7.1.3 Pembrolizumab exposure**

The dose information will be assessed by the following:

- Number of doses
- Number of cycles started per participant
- Duration of pembrolizumab exposure (in weeks) is defined by (date of last administration of pembrolizumab + 20 (200mg IV Q3W) or 41 (400mg IV Q6W) – date of first administration of pembrolizumab + 1)/7
- Actual dose (mg)
- Cumulative dose ([mg]): the cumulative dose is the sum of all actual doses of pembrolizumab, given from first to last administration
- Actual dose intensity (ADI in mg/week): defined as the cumulative dose divided by the duration of pembrolizumab exposure (in weeks)
- Planned dose intensity (PDI in mg/week): corresponds to the planned dose multiplied by the theoretical total number of doses started and divided by the theoretical cycle duration expressed in weeks (ie, 3weeks per cycle started)
- Relative dose intensity (RDI, in %):  $100 \times \frac{\text{ADI (mg/week)}}{\text{PDI (mg/week)}}$

The total number of doses, number of cycles started by participant will be summarized as a quantitative variable and by category (1-3 cycles, 4-6 cycle, ..... ,  $\geq 16$  cycles). Duration of pembrolizumab exposure, cumulative dose, ADI and RDI will be summarized quantitatively.

The following variables will be derived to describe dose modifications:

- Dose reduction: The first administration will not be counted as a dose reduction. For the second and subsequent pembrolizumab administrations, dose reduction will be determined by comparing the current dose level to the previous dose level. If the current dose level is below the dose level interval of the previous dose administration, then the current dose level is considered reduced.
- Dose omission is defined as a dose not administered at the scheduled visit but administered afterwards. “Not taken” information from eCRF dosing page to be taken into account to identify dose omissions.
- Dose delay: a dose is deemed to have been delayed if the dose is administrated up to 3 days after the theoretical date.

- Dose interruption and the reason of interruption (as collected in the eCRF). Dose will be considered interrupted if the administration is stopped during the infusion before it is completed regardless of whether it is restarted.

Dose modifications will be analyzed by participant, cycle and dose as follows:

- **Participant** (number of participants treated will be used as denominator)
  - Number (%) of participants with at least 1 dose reduction
  - Number (%) of participants with at least 1 dose omission
  - Number (%) of participants with at least 1 dose interruption
- **Cycle** (number of cycles started will be used as denominator)
  - Number (%) of cycles with at least 1 dose reduction
  - Number (%) of cycles with at least 1 dose omission
  - Number (%) of cycles with at least 1 dose interruption

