6.6 DOSE MODIFICATION

A 21-day cycle will be maintained, and dose interruption will be noted in the 21-day cycle schedule.

In the Dose Escalation cohorts, there will be no dose reductions or modifications during C1, 21-day DLT assessment period unless a DLT has occurred. After Cycle 1 and in the final dose cohort, if a dose reduction is recommended, then the SAR442720 dose level should be the previous lower dose level considered to be tolerable in prior participants receiving that dose. Two dose reductions are allowed.

In Part-2, dose reduction will be allowed for SAR442720 according to the criteria detailed below. SAR442720 may be reduced to the dose corresponding to one dose level below RP2D. Pembrolizumab dose reductions are not permitted. Pembrolizumab treatment may be interrupted or discontinued due to toxicity.

In Part-3, dose reduction for SAR442720 will be as described below. SAR442720 may be reduced to the dose corresponding to one dose level below.

In Part-4, dose reduction of SAR442720 is not allowed on C1D1, C1D15, and C2D1. For other doses, dose reduction or interruption may be allowed. Pembrolizumab dose reductions are not permitted. Pembrolizumab treatment may be interrupted or discontinued due to toxicity.

Two types of dose modifications are allowed, “dose interruption” and “dose level reduction” according to the dose modification criteria and guidelines outlined in [Section 6.6.1](#) below. Any allowed dose modification and any deviation from the intended dose (missed doses or overdoses due to participant error) should be documented on the dose eCRF.

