#### Part-2

The expansion cohort (Part-2), un-controlled, non-randomized, open-label study will assess the antitumor activity and safety of SAR442720 combined with pembrolizumab in participants with lung cancer.

Part-2 will assess the antitumor efficacy and safety of adding SAR442720 to therapeutic approaches with documented efficacy profile as 1L NSCLC therapy.

- Cohort A1: participants with PD-L1 TPS  $\geq 50\%$  NSCLC to receive SAR442720 + pembrolizumab as 1L therapy.
- Cohort A2: participants with PD-L1 TPS 1%-49% NSCLC to receive SAR442720 + pembrolizumab as 1L therapy.

Part-2 of the study will start at the RP2D for SAR442720 defined in Part-1. The SAR442720 RP2D will be 200 mg BIW, such Day 1 and Day 2 of each week, administered orally (21 days per cycle). Pembrolizumab will be administrated as a dose of 200 mg using 30 minutes IV infusion on Day 1 every 3 weeks (21 days cycle) or a dose of 400 mg using 30 minutes IV infusion on Day 1 every 6 weeks (42 days cycle).

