### 4.7.1 Extent of exposure

#### 4.7.1.1 *Overall exposure*

The dose information will be assessed by the following variables:

- Overall number of cycles started, defined by the number of cycles in which at least one dose of any study interventions is administered.
- Duration of IMP exposure (in weeks) is defined as (Last day of exposure – first day of exposure +1)/7.
- The first day of exposure is defined as the first administration date with non-zero dose for at least one of the IMP.

The last day of exposure is the day before the theoretical date of the next administration (after the last administration), defined as the maximum between:

- The last administration date + 3 for SAR442720

The last administration date + 20 for Pembrolizumab given at 200 mg IV Q3W or + 41 for Pembrolizumab given at 400 mg IV Q6W

The total number of cycles started will be summarized as a quantitative variable and by category (1-3 cycles, 4-6 cycle, ..... ,  $\geq$ 16 cycles). The duration of overall exposure will be summarized quantitatively.

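### Pembrolizumab planned dose intensity uses 3 weeks per cycle without saying which cycle is counted, so relative dose intensity on 400 mg every 6 weeks can be wrong for a fully compliant participant

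*SAP*

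**What the plan says.** SAP 1.1 (Part-2) gives pembrolizumab two regimens with two cycle lengths: "a dose of 200 mg using 30 minutes IV infusion on Day 1 every 3 weeks (21 days cycle") and "a dose of 400 mg using 30 minutes IV infusion on Day 1 every 6 weeks (42 days cycle"). The protocol synopsis and schedules of activities allow the 6-weekly regimen in Part-2 and Part-4.

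SAP 4.7.1.3 then defines the exposure variables:

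- Duration depends on the regimen. Its end point is the "date of last administration of pembrolizumab + 20 (200mg IV Q3W) or 41 (400mg IV Q6W").
- ADI is "defined as the cumulative dose divided by the duration of pembrolizumab exposure (in weeks").
- PDI "corresponds to the planned dose multiplied by the theoretical total number of doses started", divided by the "theoretical cycle duration expressed in weeks (ie, 3weeks per cycle started"). No 6-week version is given.
- RDI is 100 × ADI/PDI, and it is to be summarized quantitatively.

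The section lists the number of cycles started per participant but does not define it for pembrolizumab. SAP 4.7.1.1 does define a count, for overall exposure: it is "defined by the number of cycles in which at least one dose of any study interventions is administered". Protocol 6.6 states: "A 21-day cycle will be maintained, and dose interruption will be noted in the 21-day cycle schedule".

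**The concern.** The two parts of the RDI ratio can run on different clocks. ADI credits 42 days to each Q6W infusion. PDI credits 3 weeks to each cycle, whatever the regimen, in the same wording that SAP 4.7.1.2 uses for SAR442720, where a 3-week cycle fits. Whether the two agree for a Q6W participant depends on how many cycles are counted, which the section leaves open.

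What is at stake is how the exposure table is read. Protocol 6.6 does not permit pembrolizumab dose reductions, so a low RDI would be taken to mean missed, interrupted or late infusions. A low value produced by the formula alone could pass for a tolerability problem with the combination. Two programmers following the same text could also report different values for the same participant.

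**Working it through.** The SAP states no RDI value, so there is no figure to reproduce. The check applies its formulas to participants who receive every infusion in full and on time.

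**Inputs.** Doses and intervals are from SAP 1.1: 200 mg every 21 days and 400 mg every 42 days. The additions of 20 and 41 days and the ADI, PDI and RDI definitions are from SAP 4.7.1.3. Let n be the number of infusions and c the number of cycles started.

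**Formulas.**
- Duration (weeks) = [(n − 1) × interval + (20 or 41) + 1]/7
- ADI = dose × n / duration
- PDI = dose × n / (3 × c)
- RDI = 100 × ADI/PDI

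**Check on Q3W.** Duration = 21n/7 = 3n weeks and c = n. ADI = 200n/3n = 66.7 mg/week, PDI = 200n/3n = 66.7 mg/week, and RDI = 100% for every n. The formula works for this regimen.

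**Q6W.** Duration = 42n/7 = 6n weeks, so ADI = 400n/6n = 66.7 mg/week on every reading. PDI depends on c:

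1. *42-day cycles, or only cycles with an infusion* (c = n): PDI = 400n/3n = 133.3 mg/week. RDI = 66.7/133.3 = 50% for every n.
2. *Every 21-day study cycle, with both cycles started after each infusion* (c = 2n): PDI = 400n/6n = 66.7 mg/week. RDI = 100%.
3. *Every 21-day study cycle, with treatment ending in the first half of the last 6-week interval* (c = 2n − 1): PDI = 400n/[3(2n − 1)], so RDI = 100 × (2n − 1)/(2n).

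| n | c = 2n − 1 | PDI (mg/week) | RDI |
|---|---|---|---|
| 1 | 1 | 133.3 | 50% |
| 2 | 3 | 88.9 | 75% |
| 3 | 5 | 80.0 | 83.3% |
| 4 | 7 | 76.2 | 87.5% |

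In the third case no infusion was missed. RDI falls because ADI spreads the last dose over 42 days while the cycle count gives it 21.

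**Effect on a pooled mean.** The documents do not give the share of participants on Q6W, so the shares here are assumptions. On the first reading, mean RDI under perfect compliance is 100% − 50% × share: 87.5%, 75% and 62.5% for shares of 25%, 50% and 75%.

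**With the planned infusion interval in the denominator.** Q6W PDI = 400n/6n = 66.7 mg/week and RDI = 100% for every n. Q3W is unchanged.

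**The case against.** The strongest reply is that the study runs on 21-day cycles, so each cycle really is 3 weeks long. Protocol 6.6 says so, the schedules of activities use 21-day columns while allowing Q6W, and the only definition of cycles started in the SAP counts any cycle in which any study drug is given. SAR442720 is taken twice weekly, so every 21-day cycle would normally count. On that reading a compliant Q6W participant who starts both cycles after each infusion has an RDI of 100%.

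That part stands. A reader might infer that every compliant Q6W participant will be reported at 50%, or that the table will necessarily show severe under-dosing. The documents do not support this, because they do not settle which cycle is counted and there is real support for the 21-day count.

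The reply does not clear the formula, however. The definition of cycles started sits under overall exposure and is not carried into the pembrolizumab section, and both documents call the Q6W cycle 42 days. Even if every 21-day cycle is counted, RDI is too low whenever treatment stops after an odd number of cycles.

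The second reply is that little depends on RDI. That also stands: it is descriptive, it feeds no endpoint or analysis population, and the number of doses, cumulative dose and ADI are reported beside it and are unaffected.

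**Conclusion.** The PDI definition is wrong as written for Q6W, and the severity is minor. With 42-day cycles or infusion-only cycles, a fully compliant participant has an RDI of 50%. With all 21-day cycles, the value is 100% when 2n cycles are started, but 50% to 87.5% for 1 to 4 infusions when 2n − 1 are started. No reading gives the right value in every case, so this is more than a missing detail.

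These figures assume full doses on schedule and no change of regimen. The pooled means rest also on assumed Q6W shares and on the first reading. The effect is confined to the pembrolizumab RDI summary in Part-2 (40 participants planned) and Part-4 (up to about 12). It would go too far to call the exposure reporting as a whole uninterpretable: ADI is 66.7 mg/week for a compliant participant on either regimen and can be compared directly with the plan.

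**What to change.** In SAP 4.7.1.3, define pembrolizumab PDI as the sum of planned doses over doses started, divided by the sum of their planned infusion intervals: 3 weeks for each Q3W dose and 6 weeks for each Q6W dose. State that the study-cycle count is not used for pembrolizumab RDI. Both regimens as planned in the documents give 66.7 mg/week (200/3 and 400/6).

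Summing over doses also covers a change of regimen. For example, two Q3W doses followed by one Q6W dose give (200 + 200 + 400)/(3 + 3 + 6) = 66.7 mg/week. The SAP should add that the 20 or 41 days in the duration follow the regimen of the last infusion. Omitted or late infusions between the first and last dose would still lower RDI, because they lower ADI.

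Stating only that all 21-day cycles are counted would be a smaller edit, but it would leave the error when treatment ends mid-interval.

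The cost is a line or two of SAP text and the matching programming. The protocol's statistical section does not contain these formulas, so no protocol change is needed for this point.

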#### **4.7.2 Laboratory variables**

Hematological and clinical biochemistry toxicities will be assessed from laboratory test parameters.

A summary table will present the frequency of patients with any grade of abnormal laboratory tests and with Grade $\geq$  3 abnormal laboratory tests occurring during on-treatment period. For patients with multiple occurrences of the same laboratory variable during the treatment, the maximum grade (worst) per patient will be used. The denominator used for percentage calculation is the number of patients with at least 1 evaluation of the laboratory test during the considered observation period. For laboratory tests for which NCI-CTCAE V5.0 scale is not applicable, the frequency of evaluable patients outside normal ranges will be provided.

If relevant, selected laboratory tests will be plotted describing mean changes from baseline and associated +/- STD throughout the on-treatment period.

#### **4.7.3 Additional safety analyses (Vital signs and electrocardiograms [ECGs])**

The following vital signs and electrocardiogram (ECG) variables will be analyzed. They will be converted into standard international units.

- Vital signs: heart rate, systolic and diastolic blood pressure, weight, pulse rate, respiratory rate, pulse oximetry, and ECOG performance status
- ECG variables: heart rate, PR, QRS, QT, and corrected QTc (according to Bazett/Fridericia)/ECG assessments will be described as normal or abnormal

For vital sign variables, potentially clinically significant abnormalities (PCSA) values are defined as abnormal values considered medically important by the Sponsor according to predefined criteria/thresholds based on literature review. PCSA criteria will determine which participants had

at least 1 PCSA during the on-treatment period, taking into account all evaluations performed during the on-treatment period, including nonscheduled or repeated evaluations. The incidence of PCSA any time during the on-treatment period will be summarized.

For ECG, the incidence of participants with at least one abnormal ECG during the treatment-emergent period will be summarized regardless of the baseline level and according to the following baseline status categories:

- Normal/missing
- Abnormal

## 4.8 OTHER ANALYSES

### 4.8.1 PK analyses

Concentrations of SAR442720, pembrolizumab and adagrasib will be summarized by scheduled visit and nominal timepoint.

All concentration values below the lower limit of quantitation (LLOQ) will be treated as zero in all summary statistics excepted for the geometric mean and associated coefficient of variation for which they will be considered as missing.

For Part-3A and Part-4, PK parameter estimates, including but not limiting to the ones listed below, will be determined when possible, for SAR442720 and adagrasib:

- Maximal concentration: Cmax (observed)
- Time to reach maximal concentration: Tmax (observed)
- Area-under-the-curve from time 0 to t: AUC0-t
- Area-under-the-curve from time 0 to infinity, if possible: AUC0-inf, if possible
- t1/2, if possible
- Accumulation ratio

Unless otherwise specified, the PK parameters will be estimated based on noncompartmental analysis methods. These estimates will be summarized descriptively by dose cohort. All PK parameters will be computed using the actual elapsed time calculated relative to dose administration.

[figure not shown]
For Part-4, the geometric mean ratios and 90% confidence intervals of AUC0-inf and Cmax will be computed for SAR442720 between fed and fasted states of tablet formulation (C1D1 to C1D15) and between the tablet (test) and capsule (reference) formulations (C1D15 to C2D1). In addition, the PK parameters in Part-4 will be analyzed using a mixed effect model, which will be described in detail in the statistical analysis plan.

Population PK analysis may be conducted to obtain the PK parameters of SAR442720, pembrolizumab, and adagrasib. If performed, the results will be summarized in a separate report. Exploratory analyses may be performed to evaluate the relationship between the estimated PK parameters and PDs, selected safety, biomarker, or clinical effect endpoints.

The PK and PDy analyses will be presented in a separate report.

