- c Post-study follow-up for disease status: Participants who discontinue study intervention treatment with radiological or clinical PD at the end of a treatment visit who have not yet started treatment with another anti-cancer therapy will proceed with 3 months follow-up visits until initiation of another anti-cancer therapy, disease progression, death, or study cutoff date (whichever comes first).

Table 3 - Schedule of activities for Part-2

Procedure (Part-2)	Screening ^a		Cycle 1 (21-day cycle)			Cycles 2+ (21-day cycle)		EOT (within 30 ±5d of last dose) ^b	LTFU (every 3 months ±2 wks) ^c	Notes
Day	-1 to -28	-1 to -14	1	8 (±1 d)	15 (±1 d)	1 (±2 d)	15 (±2 d)			
Clinical Assessments										
Informed consent	X									Obtain written informed consent from the participant before any protocol required procedures and assessments are performed. Standard of care evaluations performed as part of the participant's routine treatment prior to signing consent may be used if they were done in the timeframe required for screening.
Inclusion and exclusion criteria	X									Recheck clinical status before 1st dose of study intervention.
Demography	X									Demographic information includes: age, gender, race, and ethnicity.
Full physical examination		X	X			X		X		Complete physical examination should be performed during screening, D1 of Cycle 1 and D1 of each cycle starting at C2, and at EOT. See Section 8.2.1 for details
Medical history	X									Prior cancer history includes: (i) date of diagnosis, (ii) staging, (iii) all previous therapies (ie, chemotherapy, immunotherapy, biologic or targeted agents, experimental therapies, radiotherapy, and surgery), (iv) previous therapy details (ie, regimen, start and stop dates), (v) best response for each regimen, and (vi) date of relapse or disease progression.

Procedure (Part-2)	Screening ^a		Cycle 1 (21-day cycle)			Cycles 2+ (21-day cycle)		EOT (within 30 ± 5 d of last dose) ^b	LTFU (every 3 months ± 2 wks) ^c	Notes
Day	-1 to -28	-1 to -14	1	8 (± 1 d)	15 (± 1 d)	1 (± 2 d)	15 (± 2 d)			
Past and current medical conditions	X									
Documentation of tumor genotypic mutations	X									Documentation of lack of known SHP2 inhibition resistant mutations is required. See exclusion criteria E 29 .
ECOG performance status		X	X			X		X		ECOG performance status to be assessed at screening, C1D1, and D1 of each subsequent cycle beginning at C2, and at EOT.

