Pembrolizumab dosing			Continuous dosing 200mg Q3W (or 400 mg Q6W)							Pembrolizumab is administrated in IV infusion at the hospital. See Section 6.1 .

Procedure (Part-2)	Screening ^a		Cycle 1 (21-day cycle)			Cycles 2+ (21-day cycle)		EOT (within 30 ±5d of last dose) ^b	LTFU (every 3 months ±2 wks) ^c	Notes
Day	-1 to -28	-1 to -14	1	8 (±1 d)	15 (±1 d)	1 (±2 d)	15 (±2 d)			
Assessment and documentation of study compliance			←-----→							Participants should be instructed to bring their pills and diary to every visit.
AE review		X	←-----→				X			Predose on C1D1 also see Section 8.3 .
SAE review		X	←-----→				X			Predose on C1D1 also see Section 8.3 .
Concomitant medication review		X	←-----→				X			Record all concomitant medications including any prescription medications, over-the-counter preparations, and transfusions received by participant from 7 days preceding C1D1 through EOT.
PK assessments										
Plasma samples			See Table 5 below							Blood samples (1.5 mL/sample) will be collected and processed into plasma for SAR442720 PK analysis at the time points listed in Table 5 .
Serum samples			See Table 5 below							Blood samples (1.5 mL/sample) will be collected and processed into serum for pembrolizumab PK analysis at the time points listed in Table 5 .

Abbreviations: AE = adverse event, aPTT = activated partial thromboplastin time, C = cycle, CPK = creatine phosphokinase, CT = computed tomography, ctDNA = circulating tumor DNA, D or d = day, ECG = electrocardiogram, ECHO = echocardiogram, ECOG = Eastern Cooperative Oncology Group, EOT = end of treatment, FFPE = formalin-fixed paraffin-embedded, H&E = hematoxylin and eosin, IV = intravenous, LTFU = long-term follow-up, LVEF = left ventricular ejection fraction, MRI = magnetic resonance imaging, MUGA = multigated acquisition, OCT = optical coherence tomography, PD = pharmacodynamics, PK = pharmacokinetic(s), PT = prothrombin time, PTT = partial thromboplastin time, Q3W = once every 3 weeks, Q3W = once every 3 weeks, QO = every other, RECIST = Response Evaluation Criteria in Solid Tumours, SAE = serious adverse event, SHP2 = Src Homology region 2 domain-containing protein tyrosine phosphatase 2.

WOCBP = women of child bearing potential.

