Day 8 ^d	Predose	Within 1 hour before Day 8 dose			
Day 15	Predose	Within 1 hour before Day 15 dose			
Cycle 2					
Day 1	Predose ^c	Within 1 hour before Day 1 dose	Day 1	Predose ^c	Within 1 hour before Day 1 dose
	2 hours	±10 minutes			
	8 hours ^e	±30 minutes			
Day 2 ^d	2 hours ^e	±10 minutes			
Cycle 6					
Day 1	Predose ^c	Within 1 hour before Day 1 dose	Day 1	Predose ^c	Within 1 hour before Day 1 dose
EOT	X	Any time during visit			

Abbreviations: EOT = end of treatment; PK = pharmacokinetic(s).

a PK samples = one 1.5 mL sample required per time point.

b Windows are relative to the nominal time point.

c PK samples for SAR442720 and pembrolizumab will be collected at the same time points.

d Only for Day 1, Day 2 of each weekly dosing schedule

e Only collected during Part-1.

Table 6 - PK time points (Part-3A dose escalation)

SAR442720		Adagrasib	
Study Day	PK Time points ^a	Window ^b	PK Time points ^a
Cycle 1			
Day 1	Predose	Within 1 hour before Day 1 dose	Predose
	0.5 hour ^c	±10 minutes	1 hour
	1 hour	±10 minutes	2 hours
	2 hours	±10 minutes	4 hours
	4 hours	±10 minutes	6 hours
	6 hours	±30 minutes	8 hours ^d
Day 2	12 hours ^d		Within 1 hour before D1 evening dose
	24 hours after D1 dose	Within 1 hour before Day 2 dose	12 hours after D1 evening dose
Day 8	Predose	Within 1 hour before Day 8 dose	Predose
Day 15	Predose	Within 1 hour before Day 15 dose	Predose
	0.5 hour ^c	±10 minutes	1 hour
	1 hour	±10 minutes	2 hours
	2 hours	±10 minutes	4 hours
	4 hours	±10 minutes	6 hours
	6 hours	±30 minutes	8 hours ^d
Day 16	24 hours after D15 dose	Within 1 hour before Day 16 dose	12 hours after D15 evening dose
	2 hours ^c	±10 minutes	-
Cycle 2, 3 and Cycle 4			
Day 1	Predose	Within 1 hour before Day 1 dose	Predose
EOT	X	Any time during visit	X
Abbreviations: EOT = end of treatment, PK = pharmacokinetic(s).			

a For samples where both SAR442720 and adagrasib are collected, they could be collected at the same time points.

b Windows are relative to the nominal time point.

c SAR442720 only PK samples.

d Adagrasib only PK sample, 12-hour sample on Day 1 is optional to collect.

Table 7 - PK time points (Part-3B Dose Expansion)

SAR442720			Adagrasib	
Study Day	PK Time points^a	Window^b	PK Time points^a	Window^b
Cycle 1				
Day 1	Predose	Within 1 hour before Day 1 dose	Predose	Within 1 hour before Day 1 morning dose
	2 hours ^c	±10 minutes	-	-
	6 hours	±30 minutes	6 hours	±30 minutes

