
• To assess other indicators of anti-tumor activity.• To assess the pharmacokinetic (PK) of SAR442720 in combination with pembrolizumab, and to assess the PK of pembrolizumab in combination with SAR442720.	
• Time to response (TTR) defined as the time from the first administration of investigational medicinal product (IMP) to the first documented evidence of PR or CR determined by the Investigator per RECIST v1.1 (for NSCLC).• DoR, defined as the time from first documented evidence of CR or PR until progressive disease (PD) determined by the Investigator per RECIST v1.1 or death from any cause, whichever occurs first.• Clinical benefit rate (CBR) including confirmed CR or PR at any time or stable disease (SD) of at least 6 months (determined by the Investigator per RECIST v1.1).• Disease control rate (DCR) including confirmed CR or PR or SD as determined by the Investigator per RECIST v1.1.• Progression free survival (PFS), defined as the time from the date of first IMP administration to the date of the first documented disease progression determined by the Investigator as per RECIST v1.1 or death due to any cause, whichever occurs first.• Plasma concentrations of SAR442720.• Serum concentration of pembrolizumab.

Part-3A Dose Escalation (SAR442720 and adagrasib)

	Objectives	Endpoints
Primary	
 • To define the MTD and RP2D for the combination of SAR442720 and adagrasib in participants with NSCLC and KRAS G12C mutation. • To characterize the safety and tolerability of SAR442720 in combination with adagrasib in participants with NSCLC and KRAS G12C mutation 	
 • Incidence of study drug-related DLTs in Cycle 1. • Incidence, nature, and severity of TEAEs and SAEs, graded according to NCI CTCAEv5.0 for the combination of SAR442720 and adagrasib.
Secondary	
 • To characterize the PK of SAR442720 in combination with adagrasib, and to characterize the PK of adagrasib in combination with SAR442720. • To estimate the anti-tumor effects of SAR442720 in combination with adagrasib in all participants 	
 • PK parameters of SAR442720 (C_{max}, T_{max}, AUC_{0-last}) • PK parameters of adagrasib (C_{max}, T_{max}, AUC_{0-last}) • ORR and DoR of SAR442720 and adagrasib in all participants. ORR of combination therapy with SAR442720 and adagrasib will be based on RECIST v1.1.

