Part-2 of the study will start once RP2D for SAR442720 from Part-1 is confirmed. The SAR442720 RP2D will be 200 mg BIW, Day 1 and Day 2 of each week, administered orally (21 days per cycle). This dose emerged as the safe dose of SAR442720 from the escalation part (Part-1) of this study. Pembrolizumab will be administered as a dose of 200 mg using a 30 minutes IV infusion on Day 1 every 3 weeks (21 days cycle) or a dose of 400 mg using a 30 minutes IV infusion on Day 1 every 6 weeks (42 days cycle).

The duration of the study for a participant will include:

- Screening period: up to 28 days.
- Treatment Period: enrolled participants will receive continuous treatment until PD, unacceptable AE, other full permanent discontinuation criteria as described in [Section 7.1](#).
- End of Treatment and Follow-up: EOT visit will occur 30 days ± 5 days from last IMP administration or prior to initiation of further therapy. Participants will then enter the Observation period and will be followed differently depending on the reason leading to EOT:

- Participants who discontinue study treatment with radiological or clinical PD (per RECIST v1.1) or iCPD (per iRECIST) will be followed in the Follow-Up Visit 1 occurring 3 months \pm 5 days from last IMP administration, or until start of new anticancer therapy or cohort cut-off, whichever comes first, before moving to the Survival Phone Call Follow-Up Period.

Part-3

Part-3 of this open-label, multi-center, un-controlled, non-randomized study, will assess the safety, RP2D, anti-tumor activity, and PK of SAR442720 in combination with adagrasib in participants with NSCLC harboring KRAS G12C mutation.

Part-3A

SAR442720 and adagrasib will be administered orally on a continuous basis. The starting dose (DL1) of SAR442720 will be 100 mg on Day 1 and Day 2 BIW with adagrasib given at 400 mg BID orally. The dose escalation will follow the mTPI2 design with a minimum of 3 participants evaluable for DLT for each dose level. Participants will be DLT-evaluable if they have taken at least 80% of the scheduled Cycle 1 dose of both drugs in the first 21 days of treatment. The same mTPI-2 design as that used in Part-1 will be used in Part-3A.

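### SAP 4.8.1 has no split of pembrolizumab concentrations by regimen, so Part-2 summary rows can mix 200 mg Q3W and 400 mg Q6W values that are not alike

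*SAP*

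**What the plan says.** **Regimens.** The pembrolizumab dosing row of the Part-2 Schedule of Activities (Protocol section 1.3, Table 3) reads "Continuous dosing 200mg Q3W (or 400 mg Q6W"). Neither document says how many participants will receive each regimen.

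**Objective.** A Part-2 secondary objective in Protocol section 3 is "to assess the PK of pembrolizumab in combination with SAR442720". Its endpoint is the serum concentration of pembrolizumab.

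**Sampling.** Protocol Table 5 has one pembrolizumab schedule for both regimens: C1D1 before the dose and just after the infusion, then C2D1 and C6D1 before the dose. The C2D1 and C6D1 samples are labelled predose and timed to the hour before the Day 1 dose. A footnote states that "PK samples for SAR442720 and pembrolizumab will be collected at the same time points".

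**Analysis.** SAP section 4.8.1 says "Concentrations of SAR442720, pembrolizumab and adagrasib will be summarized by scheduled visit and nominal timepoint". SAP section 4.1 presents Part-2 by PD-L1 cohort, and Protocol section 9.4.1 by cohort and overall. Neither mentions the pembrolizumab regimen.

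**Cycle length.** The Part-2 Schedule of Activities is headed "Cycles 2+ (21-day cycle"). Protocol section 6.6 says "A 21-day cycle will be maintained, and dose interruption will be noted in the 21-day cycle schedule". SAP section 4.7.1.3, which covers both regimens, defines planned dose intensity as a quantity "divided by the theoretical cycle duration expressed in weeks (ie, 3weeks per cycle started"). Against these, Protocol section 4.1 describes the longer regimen as "a dose of 400 mg using a 30 minutes IV infusion on Day 1 every 6 weeks (42 days cycle"); the synopsis and SAP section 1.1 use similar wording.

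**The concern.** A row of concentrations by visit can be read only if the values in it share a dose and a time since that dose. In Part-2 they need not. The two regimens differ twofold in dose and twofold in interval, while the sampling table and the summary rule treat them as one.

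At stake is the reading of the planned table for a named secondary endpoint. The pooled mean would move with the proportion of participants on Q6W, which has nothing to do with SAR442720. A row labelled predose would also invite comparison with troughs when some of its values may not be troughs.

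**Working it through.** The plan states no expected concentration for pembrolizumab, so there is no figure to reproduce. The check is a calendar followed by simple superposition.

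**Step 1: calendar with 21-day cycles** (Table 3, Protocol section 6.6, SAP section 4.7.1.3)
- C2D1 = 1 + 21 = day 22. C6D1 = 1 + 5 × 21 = day 106.
- Q3W doses fall on days 1, 22, 43, 64, 85 and 106. Both samples are 21 days after the previous dose with a dose due, so both are 3-week troughs.
- Q6W doses fall on days 1, 43, 85 and 127. The previous doses are on days 1 and 85, so both samples are 21 days into a 42-day interval with no pembrolizumab dose due.

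**Step 2: calendar with 42-day cycles for Q6W** (Protocol section 4.1, SAP section 1.1)
- C2D1 = 1 + 42 = day 43. C6D1 = 1 + 5 × 42 = day 211.
- Both samples are 42 days after the previous Q6W dose, so they are 6-week troughs. They share a row with 3-week troughs from days 22 and 106.

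**Step 3: size on the 21-day calendar**

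Assumptions: one compartment, linear PK, and a half-life of 14 to 28 days (not in the documents). Let x be the fraction remaining after 21 days, x = 2^(−21/half-life).
- C1D1 after infusion: 400/200 = 2.
- C2D1: 400x / 200x = 2 at any half-life.
- C6D1: 400(x + x³ + x⁵) / 200(x + x² + x³ + x⁴ + x⁵):
  - half-life 14 days, x = 0.354: 2 × 0.4033 / 0.5439 = 1.48
  - half-life 21 days, x = 0.500: 2 × 0.6563 / 0.9688 = 1.35
  - half-life 28 days, x = 0.595: 2 × 0.8792 / 1.3577 = 1.30

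**Step 4: pooled mean**

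With a Q6W share f and a ratio r, the pooled mean is 1 + f(r − 1) times the Q3W trough mean. The share is not in the documents, so 25%, 50% and 75% are illustrations.
- C2D1 (r = 2): 25%, 50% and 75% above the Q3W trough mean.
- C6D1 (r = 1.30 to 1.48): 7 to 12%, 15 to 24% and 22 to 36% above it.
- With f = 0 or f = 1 there is no mixing.

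**Step 5: size on the 42-day reading**
- C2D1: 400x² / 200x = 2x, which is 0.71, 1.00 and 1.19 for half-lives of 14, 21 and 28 days.
- C6D1: 400(x² + x⁴ + x⁶ + x⁸ + x¹⁰) / 200(x + x² + x³ + x⁴ + x⁵), which is 2 × 0.1429 / 0.5439 = 0.53 at 14 days and 2 × 0.5439 / 1.3577 = 0.80 at 28 days.

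So the mixing remains on either calendar, but its size and even its direction depend on which one sites follow.

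**Step 6: does another rule separate the regimens?** SAP section 4.8.1 also refers to dose cohorts and to actual elapsed time. Both rules govern PK parameters, which are listed for SAR442720 and adagrasib in Part-3A and Part-4. They do not reach Part-2 pembrolizumab concentrations. Population PK analysis is optional and would be reported separately.

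**The case against.** **The SAP is silent; it does not order pooling.** This stands in part. Nothing in SAP section 4.8.1 forbids a split, and PK results go into a separate report. But the stated rule gives one row per visit and time point. The SAP does separate the regimens elsewhere: section 4.7.1.3 adds 20 days for Q3W and 41 for Q6W when computing exposure. The omission in 4.8.1 is therefore worth closing.

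**The data are not lost.** This stands. A reader might infer that the Part-2 pembrolizumab PK data cannot be interpreted. The documents do not support that: Protocol section 8.5 records the actual date and time of each sample, and section 6.4 those of each dose given in clinic. The values can be separated with nothing new collected. Under linearity, dividing by dose would even remove the C2D1 difference on the 21-day calendar.

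**The mid-interval timing is not certain.** This stands. A reader might take it as settled that no Q6W dose is due at C2D1 or C6D1. The 21-day calendar has the firmer support, but the 42-day wording contradicts it. So does the Part-4 text in Protocol section 4.1, where every participant receives pembrolizumab on C2D1 although Q6W is allowed.

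**The endpoint is modest.** This stands. A reader might see it as a test of whether SAR442720 alters pembrolizumab PK. There is no control arm, Protocol section 9.1 sets no hypothesis, and only descriptive summaries are planned. Protocol section 2.3.1.3 rates the interaction potential as low.

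**Conclusion.** The concern holds in a limited form. Part-2 allows two pembrolizumab regimens, samples them on one schedule and summarises them by visit with no split. On the 21-day calendar the C2D1 and C6D1 rows combine 3-week troughs with day-21-of-42 values. On the 42-day reading they combine 3-week with 6-week troughs. The C1D1 end-of-infusion row combines 200 mg with 400 mg on either reading.

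The twofold ratio at C2D1 needs only linear PK and the 21-day calendar. The 1.3 to 1.5 range at C6D1 also needs the assumed half-life. The shift in any pooled mean cannot be fixed without the Q6W share.

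The consequence is confined to a descriptive secondary PK endpoint in a part planned for 40 participants. Response and safety analyses are untouched. Table 8 repeats the C2D1 and C6D1 pattern for Part-4, but pembrolizumab PK is not a Part-4 objective, so that adds little.

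**What to change.** **SAP section 4.8.1.** State that pembrolizumab concentrations are summarised separately for 200 mg Q3W and 400 mg Q6W, by time since the last pembrolizumab dose. Do not label a Q6W sample predose where no pembrolizumab dose is due. This is a sentence or two applied to data already recorded. The cost is fewer participants per summary row.

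**Protocol and SAP wording.** Reconcile the 21-day cycle text (Table 3, Protocol section 6.6, SAP section 4.7.1.3) with the 42-day cycle text (synopsis, Protocol section 4.1, SAP section 1.1). Reconcile the Part-4 statement about pembrolizumab on C2D1 with the Q6W option and with Tables 5 and 8. Which wording is right is for the sponsor to settle.

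**Optional.** On the 21-day calendar no Q6W trough is scheduled, and the sponsor may wish to consider one. Moving the Q6W samples to C3D1 and C7D1 is not part of the required change. It would give up the one post-Cycle-1 time since dose that both regimens share, and the pairing with SAR442720 samples. It may also come too late for Part-2, since the SAP was approved ahead of database lock for the expansion cohort.
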